## 8.0 STUDY OR STUDY SITE TERMINATION

If the Sponsor, Investigator, Medical Monitor, study monitor, or appropriate regulatory officials discover conditions arising during the study that indicate that the study should be halted or that the study center should be terminated, this action may be taken after appropriate consultation. Nektar Therapeutics has the right to terminate this study at any time for any reason. Conditions that may warrant termination of the study include, but are not limited to, the following:

- The discovery of an unexpected, serious, or unacceptable risk to the subjects enrolled in the study
- A decision on the part of the Sponsor to suspend or discontinue testing, evaluation, or development of the study drug

A study or study site may also warrant termination under the following conditions:

- Failure of the Investigator to comply with pertinent regulations of appropriate regulatory authorities
- Recording of inaccurate or incomplete data
- Submission of knowingly false information from the research facility to the Sponsor, Study Monitor, or appropriate Regulatory Authority
- Insufficient adherence to protocol requirements
- General Good Clinical Practice (GCP) noncompliance as determined by the Sponsor

In the event that the clinical development of the investigational product is discontinued, Nektar Therapeutics shall immediately inform all study Investigators/institutions and Regulatory Authorities. Study termination and follow up will be performed in compliance with the conditions set forth in the ICH sixth efficacy publication (E6) on GCP and local regulatory requirements.

## 9.0 ASSESSMENT OF SAFETY OR ADVERSE EVENTS AND SERIOUS ADVERSE EVENTS

In this section, the term study drug refers to NKTR-102 for Injection.

### 9.1 Adverse Event Definition and Assessment

An AE is defined as any untoward medical occurrence associated with the use of a drug in humans, whether or not considered drug related. An AE can therefore be any unfavorable and unintended sign, symptom, or disease temporally associated with the use of a medicinal product, whether or not considered related to the medicinal product. An AE can also arise from any use of the drug and from any route of administration, formulation, or dose. This definition includes intercurrent illnesses or injuries, and exacerbation of preexisting conditions as well as events attributed to protocol-mandated procedures. Clinical laboratory abnormalities will only be reported as AEs if they are deemed clinically significant by the Investigator and/or are associated with signs and symptoms, require treatment, or require follow-up.

An unexpected AE is one of a type not consistent in nature or severity with information in the current IB.

An AE does not include:

- A medical or surgical procedure (e.g., surgery, endoscopy, tooth extraction, or transfusion); an AE is the underlying condition that leads to the procedure
- Pre-existing diseases or conditions present or detected before start of study drug administration and which do not worsen or increase in severity or frequency after the administration of study drug
- Situations where an untoward medical occurrence has not occurred (e.g., hospitalization for elective surgery for a condition that has not worsened on study, social and/or convenience admissions to grant families a respite in caring for a subject)

### 9.2 Monitoring Adverse Events

All AEs will be assessed by the Investigator and recorded in the appropriate case report form (CRF), including but not limited to, the date of onset and resolution, seriousness, severity, relationship to study drug, outcome, and action taken with study drug. Adverse events will be reported starting immediately after the subject or subject's legal representative has provided written informed consent through the End-of-Treatment visit (30 ± 7 days from the last dose of study drug in the extension study).

After providing informed consent for the extension study, if the subject is continuing in the original protocol and therefore will not have received the first dose of study drug in the extension study (Protocol 11-PIR-09), any AEs that occur will be collected under the original protocol. For subjects who have ended the original protocol and have provided informed consent for the extension study (Protocol 11-PIR-09), AEs will be collected under the extension study (Protocol 11-PIR-09).

Adverse events that were considered related to study drug in the original protocol and were ongoing when the subject ended the original protocol will be captured as a new AE in the extension study (Protocol 11-PIR-09) marked as continuing. Unrelated AEs that were ongoing at the end of the original protocol may also be captured as new AEs in the extension study (Protocol 11-PIR-09) marked as continuing.

For each AE, the following data elements will be recorded on the CRFs:

- Verbatim description of event
- NCI-CTCAE v. 4.0 grade for AE severity (refer to Section 9.3)
- Start and stop date of AE
- Relationship/causality attribution to study drug
- Whether or not the administration of study drug was reduced, interrupted, delayed, or permanently discontinued due to the AE
- Whether or not the event was considered as an SAE
- Treatment provided for the AE (pharmacologic or non-pharmacologic)
- Outcome of the AE

### 9.3 Grading of Adverse Events

The severity of an event and the seriousness are not to be considered synonymous. The severity is grading the intensity of an event. The seriousness of event is based on the subject/event outcome or action criteria. All AEs will be assessed for severity using the NCI-CTCAE version 4.0. If a particular AE is not listed in the NCI-CTCAE, the following criteria will be used to assess severity by the Investigator:

- grade 1 = Mild (asymptomatic or mild symptoms or clinical or diagnostic observations only, intervention not indicated)

- grade 2 = Moderate (minimal, or local or non-invasive intervention indicated or limiting age-appropriate instrumental activities of daily living [ADL])
- grade 3 = Severe (medically significant but not immediately life-threatening or hospitalization or prolongation of hospitalization indicated or disabling, limiting self care ADL)
- grade 4 = Life threatening or disabling (life threatening consequences, urgent intervention indicated)
- grade 5 = Death (related to AE)

Adverse events will be reported using the maximal severity grade experienced for that continuing instance of the AE. Please refer to the CRF Completion Guidelines for detailed reporting instructions.

#### **9.4 Causality Relationship of Adverse Events**

The relationship of each AE to the study drug will be evaluated by the Investigator using the following definitions:

- Not related: The AE is clearly not related to the study drug(s). The AE can be explained to be likely related to other factors such as concomitant medications or the subject's clinical state.
- Unlikely related: The AE is doubtfully related to study drug(s). The current knowledge or information about the AE indicates that a relationship to the study drug is unlikely.
- Possibly related: The AE may be related to the study drug(s). A plausible temporal sequence exists between the time of administration of the study drug and the development of the AE and it follows a known response pattern to the study drug. The reaction may have been produced by the subject's clinical state or other concomitant therapies or interventions.
- Definitely related: The AE is clearly related to the study drug(s). A plausible temporal sequence exists between the time of administration of the study drug and the development of the AE and it follows a known response pattern to the study drug. The AE cannot be reasonably explained by the known characteristics of the subject's clinical state or other concomitant therapies or interventions administered to the subject.

The causality criteria of definitely related and possibly related will be considered related to the study drug as applicable for regulatory reporting requirements.

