## **2.2 Study Rationale**

This study is designed to allow an extension period of NKTR-102 therapy for subjects who previously received NKTR-102 during a clinical study and are without signs of disease progression since receiving NKTR-102.

The estimated study duration is approximately 5 years. The duration of treatment in this study is estimated to be approximately 2 years. Subjects may continue to receive repeated cycles of study drug treatment until progression of disease, unacceptable toxicity, death, withdrawal by subject, Investigator decision, lost to follow-up, or study is terminated by the Sponsor. Since this trial may involve the longest exposure to NKTR-102 to date, it will allow for the collection of safety data, particularly serious adverse events (SAEs) that may appear only after long-term exposure to NKTR-102.

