## 9.5 Adverse Event Reporting and Follow-up

All AEs will be followed until resolution or until  $30 \pm 7$  days after last dose of study drug administration, whichever is earlier, except related AEs which will be followed until they stabilize or resolve; until the Investigator assesses the event as chronic or stable; start of new cancer therapy; subject lost to follow-up or subject death, whichever is earlier. If an unrelated AE has not completely resolved up to  $30 \pm 7$  days after last dose of study drug, the final outcome of these ongoing AEs will be captured as “Not Recovered/Not Resolved” or “Recovering/Resolving”, whichever is applicable.

Any new AEs occurring more than  $30 \pm 7$  days after last dose of study drug will be captured only if serious and assessed by the Investigator as related (possibly/definitely related) to study drug (i.e. a related SAE). For specific instructions on identifying and reporting SAEs, see Sections 9.6 and 9.7 below.

This study will use the MedDRA for coding all AEs.

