### **9.9 Expedited Reporting of SAEs**

A SUSAR is a SAE that is considered "unexpected" and assessed as related to the study drug by the Investigator or the Sponsor. All SAEs deemed related to the study drug and not expected based on the most current IB are subject to expedited reporting by the Sponsor to the applicable Regulatory Authorities. Therefore, the investigator or study site personnel must report all SAEs

to Nektar Therapeutics Drug Safety or its designee within **24 hours** of first becoming aware of the event.

Fatal or life-threatening SUSARs will be reported by the Sponsor to the Regulatory Authorities as soon as possible, but no later than 7 calendar days after Sponsor or Sponsor's designee has first knowledge of the minimum criteria for expedited reporting. Non-fatal or non-life-threatening SUSARs will be reported to the Regulatory Authorities, IRBs/IECs, and Investigators as soon as possible, but no later than 15 calendar days after Sponsor or Sponsor's designee has first knowledge of the SUSAR.

Reporting of SUSARs to all applicable Regulatory Authorities will be done by Nektar Therapeutics Drug Safety or designee as per local country and regional regulations.

Notification of SUSARs to the central IRBs will be done by Nektar Therapeutics Clinical Operations or designee in accordance with the SOPs and policies of the IRBs. Reporting to local IRBs will be done by the applicable study site personnel as per their institutional guidelines. Adequate documentation must be provided to Nektar Therapeutics Clinical Operations or designee, showing that the local IRB was properly notified.

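### Section 9.4 requires a known response pattern for both related categories, so a new type of toxicity has no fitting causality category and attribution will lean toward unrelated

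*Protocol*

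**What the plan says.** Protocol section 9.4 tells the Investigator to grade causality with four definitions. *Possibly related* and *definitely related* share one criterion: plausible timing between administration and "the development of the AE and it follows a known response pattern to the study drug". The two conditions are joined by *and*, and no other route is offered. *Unlikely related* is met when "The current knowledge or information about the AE indicates that a relationship to the study drug is unlikely". *Not related* is for events that clearly have no connection to the drug. The section closes: "The causality criteria of definitely related and possibly related will be considered related to the study drug as applicable for regulatory reporting requirements".

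Other sections rely on that grading or bear on it:

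- Section 2.2 gives as a benefit of the study the collection of safety data, "particularly serious adverse events (SAEs) that may appear only after long-term exposure to NKTR-102".
- Section 9.1: "An unexpected AE is one of a type not consistent in nature or severity with information in the current IB".
- Section 9.5: a new AE more than 30 ± 7 days after the last dose "will be captured only if serious and assessed by the Investigator as related". Section 9.7 applies the same condition to SAEs beyond 30 days.
- Sections 9.5 and 9.8 stop follow-up of unrelated events at 30 ± 7 days after the last dose, or at resolution if earlier.
- Section 9.9 defines a SUSAR as an SAE that is unexpected "and assessed as related to the study drug by the Investigator or the Sponsor".
- Section 12.2 tabulates AEs by preferred term, organ class, severity and relationship, with by-subject listings and no formal testing.

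**The concern.** The study may give the longest exposure to NKTR-102 so far, and its rationale is partly to find harms that shorter trials could not show. Some of those harms may be of a kind not seen before. For exactly these events the causality definitions ask for something that cannot yet exist, a known pattern of response to the drug.

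Section 12.2 names safety as the primary endpoint and plans descriptive output only, so the tables are the result. If the Investigator's label is unreliable for new toxicities, the tables by relationship are unreliable where they matter most. The label also acts as a gate: it decides whether a late event enters the database and how long an earlier one is followed.

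**Working it through.** No power or sample-size figure is involved. The check is to run one hypothetical event through the definitions, then trace what depends on the answer. Take an event of a type never seen with NKTR-102, with plausible timing and no obvious other cause.

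| Category (9.4) | What it asks for | Does the event meet it? |
|---|---|---|
| Definitely related | Timing, known pattern, no other reasonable explanation | No: no known pattern |
| Possibly related | Timing and known pattern; other causes may have contributed | No: no known pattern |
| Unlikely related | Doubtful link; current knowledge points against one | Not clearly: there is no knowledge either way |
| Not related | Clearly unconnected; likely due to other factors | No: nothing makes it clear |

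So no category fits. The opening sentence of *possibly related* says only that the drug may be the cause, and some Investigators will stop there. Others will apply the explicit two-part criterion that follows and move the event down. Because that written criterion bars only the related categories, the disagreement between sites is not symmetric: it pulls toward unrelated.

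**Conflict with 9.1 and 9.9.** An event unexpected in nature is one whose type is not consistent with the Investigator's Brochure. A SUSAR must be unexpected and related. Under the literal wording of 9.4, an Investigator cannot assign a related category to an event whose type is new, although 9.9 presupposes that such events arise.

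**What depends on the label.**

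| Item | Depends on the Investigator's label? |
|---|---|
| AEs from consent through End-of-Treatment (9.2) | No, all recorded |
| SAEs with onset within 30 days of last dose (9.7) | No, all reported |
| Deaths (9.6) | No, all reported |
| New events beyond 30 ± 7 days (9.5), SAEs beyond 30 days (9.7) | Yes |
| Follow-up past 30 ± 7 days (9.5, 9.8) | Yes |
| Tables by relationship (12.2) | Yes |

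Section 9.8 is not clean on follow-up: its opening sentence carries all SAEs to resolution or end of study, while its last paragraph stops unrelated ones at 30 ± 7 days. Section 9.9 likewise tells sites to report every SAE, with no time limit, which does not match the filter in 9.5 and 9.7. Neither is a dependable safeguard as written.

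**Is onset after the filter starts plausible?** Sections 2.1 and 2.1.2.3 give an apparent SN38 half-life of about 40 days. Assuming simple exponential decline, the fraction remaining at day *t* is 0.5^(*t*/40):

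- day 30: 0.5^(30/40) = 0.59
- day 37: 0.5^(37/40) = 0.53

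More than half the SN38 level would still be present when capture starts to depend on the label. This shows only that later onset is not far-fetched; it does not estimate how often it happens.

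**The case against.** The strongest reply is that most of the safety data do not pass through this gate. Section 2.2 speaks of harm after long exposure, not harm after the last dose. Treatment is estimated at about 2 years, and a new SAE during that time is recorded, appears in the tables by term, organ class and severity, is listed by subject, and reaches the Safety Review Committee, whose review of SAEs carries no stated relatedness limit (9.10). This stands. A reader might infer that the safety signal as a whole is lost; the documents do not support that. The related subset, follow-up and late capture are affected.

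Second, a reader might infer that a new toxicity becomes unrelated by definition, so that none could ever be counted as related. Section 9.4 does not say so. The lower two categories have their own conditions, which the event does not clearly meet, and the opening sentence of *possibly related* invites a looser reading. Section 9.4 also does not equate a known pattern with listing in the Investigator's Brochure, and a known toxicity that appears late, or is unexpected in severity or frequency (9.6), can still qualify. The defect is a gap with a predictable lean, not a forced outcome.

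Third, section 9.9 lets the Sponsor judge relatedness. That helps expedited reporting of events the Sponsor hears about. It does not change the Investigator's label used in 9.5, and under the 9.5 and 9.7 filter a late event judged unrelated need not reach the Sponsor.

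Finally, the primary objective is access, and the CRF Completion Guidelines cited in 9.3 are not among the documents; they may contain a clarification. Both points temper the weight of the concern, but the protocol should not depend on an unseen guideline to correct its own definition.

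**Conclusion.** The point holds as a defect of wording with limited but real consequences. For a new type of toxicity with plausible timing, section 9.4 offers no category that clearly applies. Investigator attribution will therefore vary and lean toward unrelated, against the purpose stated in 2.2 and the unexpected-and-related concept in 9.9.

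Loss of capture is confined to new SAEs beyond 30 ± 7 days after the last dose. For earlier events the harm is shortened follow-up and under-counting in the tables by relationship.

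No numerical size can be given. It is tempting to calculate the chance that at least one such event occurs among the planned maximum of 150 subjects, but the documents give no incidence for an unknown toxicity. The result would also be a chance of occurrence, not of loss or misclassification.

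The conclusion assumes that at least some Investigators apply the definitions as written, and that no guideline outside the protocol overrides them.

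**What to change.** In section 9.4, delete the known-response-pattern condition from *possibly related*. Define the category as a reasonable possibility of a causal relationship, judged on timing together with other evidence, for example biological plausibility, dechallenge or rechallenge, and alternative causes. State that a known pattern supports a causal link but is not required. *Definitely related* can keep its stricter wording, since *possibly related* is enough to count as related. Align the CRF guideline.

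Timing alone should not be made sufficient. With dosing every 21 days and an SN38 half-life of about 40 days, nearly every on-treatment AE has plausible timing, and the category would stop discriminating.

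The cost is a short protocol amendment and a matching guideline edit. Some more events will be classed as related, with longer follow-up for those, and events graded before and after the change will not be strictly comparable. Section 6.7 and Table 4 also use drug-relatedness, so the clinical team should confirm that those rules still read as intended under the revised definition.

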## 9.5 Adverse Event Reporting and Follow-up

All AEs will be followed until resolution or until  $30 \pm 7$  days after last dose of study drug administration, whichever is earlier, except related AEs which will be followed until they stabilize or resolve; until the Investigator assesses the event as chronic or stable; start of new cancer therapy; subject lost to follow-up or subject death, whichever is earlier. If an unrelated AE has not completely resolved up to  $30 \pm 7$  days after last dose of study drug, the final outcome of these ongoing AEs will be captured as “Not Recovered/Not Resolved” or “Recovering/Resolving”, whichever is applicable.

Any new AEs occurring more than  $30 \pm 7$  days after last dose of study drug will be captured only if serious and assessed by the Investigator as related (possibly/definitely related) to study drug (i.e. a related SAE). For specific instructions on identifying and reporting SAEs, see Sections 9.6 and 9.7 below.

This study will use the MedDRA for coding all AEs.

## 9.6 Serious Adverse Event Definition

An SAE is defined as any untoward medical occurrence that at any dose:

- Results in death
- Is life threatening, i.e., in the opinion of the investigator, the AE places the subject at immediate risk of death from the event as it occurred; it does not include a reaction that, had it occurred in a more severe form, might have caused death.
- Requires inpatient hospitalization or prolongation of an existing hospitalization that occurs during the course of a subject’s participation in a clinical study, except for those due to the following:
  - A surgery or procedure that was planned before the subject entered the study and which is part of the planned study procedure
  - Nonmedical reasons, in the absence of an AE
- Results in persistent or significant disability or incapacity
- Is a congenital anomaly or birth defect

- Is an important medical event that, based upon appropriate medical judgment, may jeopardize the subject and may require medical or surgical intervention to prevent one of the other outcomes listed above

An unexpected SAE is any SAE in which the nature, frequency or severity is not consistent with that indicated in the IB.

Death is an outcome of an AE, and not an AE in itself. All deaths regardless of causality must be reported. An efficacy failure is not considered an SAE. “Life-threatening” means that the subject was at immediate risk of death from the event as it occurred. This does not include an event that might have led to death, if it had occurred with greater severity. “Inpatient hospitalization” means the subject has been admitted to a hospital for medical reasons for any length of time. The Investigator should attempt to establish a diagnosis of the event based on signs, symptoms, and/or other clinical information. In such cases, the diagnosis should be documented as the AE and/or SAE and not the individual signs/symptoms.

### 9.7 Serious Adverse Event Reporting

All SAEs with an onset within **30 days** after the subject’s last dose of study drug, whether or not considered related to study drug treatment, will be reported to Nektar Therapeutics Drug Safety or its designee within **24 hours** of when the site becomes aware of the event. In addition, SAEs that are assessed by the Investigator as related to NKTR-102 and occurring **> 30 days** after last dose of study treatment will also be reported to Nektar Therapeutics Drug Safety or its designee within **24 hours** of when the site becomes aware of the event.

[REDACTED]

The Investigator must complete the SAE Report Form, assess the causality relationship to the study treatment as applicable, and send the completed SAE form by fax to Nektar Therapeutics Drug Safety or designee.

A follow-up report and any additional records (such as hospital records, consultant reports, and autopsy findings) will be faxed to Nektar Therapeutics Drug Safety or designee as soon as these documents become available or promptly upon request.

Any medication or other therapeutic measures used to treat the event will be recorded.

All SAEs will be followed as described in Section **9.8** below.

Pregnancy, although reportable, is not considered an AE/SAE unless a male subject's female partner experienced signs or symptoms of pregnancy complications. Females who become pregnant will be followed every trimester until the outcome of the pregnancy is known. Pregnancy follow-up should describe the outcome of the pregnancy, including any voluntary or spontaneous termination, details of the birth, and the presence or absence of any congenital abnormalities or birth defects in the offspring.

Reporting of SAEs to the IRB/IEC will be done in accordance with the standard operating procedures and policies of the IRB/IEC. Adequate documentation must be provided to Nektar Therapeutics, showing that the IRB/IEC was properly notified. Serious adverse events will be reported by Nektar Therapeutics or designee to the regulatory authorities, per local regulations.

